27.4.4 Safety

Safety and tolerability will be assessed in terms of frequency and types of AEs, and changes in laboratory data, vital signs, and ECG, when compared to baseline.

Adverse events will be listed individually by participant and treatment period, separately for Cycle 1 and for other treatment cycles. The number of participants experiencing each AE will be summarised by the Medical Dictionary for Regulatory Activities (MedDRA) system organ class, MedDRA preferred term and CTCAE grade, with the exception of clinical TLS which will use both CTCAE grade and Cairo-Bishop criteria (Howard modification); see [Appendix F](#)). The number and percentage of participants with AEs in different categories (eg, causally related and CTCAE Grade ≥ 3) will be summarised by treatment period, and events in each category will be further summarised by MedDRA system organ class and preferred term. SAEs will be summarised separately if a sufficient number occur.

AE summary tables will include only treatment-emergent AEs. AEs will be defined as treatment-emergent if they have an onset or worsen (by Investigator report of a change in intensity/severity), during the study treatment until 30 days from the last dose of any study intervention, but prior to subsequent cancer therapy. AEs occurring outside this period will be flagged in listings.

Haematology, clinical chemistry, coagulation, vital signs, ECG data, and other laboratory values will be listed individually by participant and suitably summarised. For all laboratory variables, which are included in the current version of CTCAE, the CTCAE grade will be calculated.

Details of any deaths will be listed for all participants.

Graphical presentations of safety data will be presented as is deemed appropriate. This may include, but is not restricted to, presentation of parameters against time,

concentration, or shift plots. Appropriate scatter plots will also be considered to investigate trends in parameters compared to baseline level.

ECG Changes

QTc will be calculated using Fridericia's formula.

Creatinine Clearance

Estimated creatinine clearance will be calculated using the Cockcroft and Gault formula.

Other Significant Adverse Events

During the evaluation of the AE data, an AstraZeneca medically qualified expert will review the list of AEs that were not reported as SAEs and AEs leading to discontinuation of study treatment. Based on the expert's judgement, AEs of particular clinical importance may, after consultation with the Global Safety Physician, be considered OAEs and reported as such in the CSR. A similar review of laboratory values, vital signs, ECGs, and other safety assessments will be performed for identification of OAEs.

Examples of these are marked haematological and other laboratory abnormalities, and certain events that lead to intervention (other than those already classified as serious), dose reduction or significant additional treatment.

27.4.5 Efficacy

Tumour response data will be listed and summarised by treatment period, using the standard response criteria as defined in Section [26.4.1](#).

For Part A participants, all efficacy endpoints are exploratory. Planned analysis of exploratory endpoints will be outlined in the SAP.

27.4.5.1 Objective Response Rate and Proportion of Participants with Complete Response

The ORR is defined as the proportion of participants who achieve either a CR or PR, according to the Lugano Response Criteria for Non-Hodgkin's Lymphoma ([Cheson et al 2014](#)). Data obtained from first dose of study treatment up until progression, or the last evaluable assessment in the absence of progression, will be included in the assessment of ORR, regardless of whether the participant withdraws from therapy. Participants who discontinue treatment without a response or progression, receive a subsequent therapy, and then respond will not be included as responders in the ORR.

ORR and proportion of participants with CR will be presented with corresponding 80% and 95% two-sided CIs.

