24.4 Duration of Therapy

Participants will move from AZD4573 monotherapy to combination treatment (AZD4573 + acalabrutinib) based on the Lugano overall response ([Table 36](#)) ([Cheson et al 2014](#)).

Table 29 **Part A - Duration of AZD4573 Monotherapy**

Disease Assessment	Lugano 2014 Overall Response	Treatment	Next Scheduled Disease Assessment
Period 1, Cycle 2, Week 3 ^a	CR	Continue AZD4573 monotherapy (Period 1, Cycle 3)	Period 1, at Cycle 5, Week 3
	PR	Continue AZD4573 monotherapy (Period 1, Cycle 3)	Period 1, at Cycle 5, Week 3
	SD	Continue AZD4573 monotherapy (Period 1, Cycle 3) ^b	Period 1, at Cycle 5, Week 3
	PD	Start combination therapy (Period 2, Cycle 1)	Period 2, after 2 cycles (Section 26.4.2)
Period 1, Cycle 5, Week 3 ^a	CR	Continue AZD4573 monotherapy (Period 1, Cycle 6)	Period 1, after 8 cycles (Section 26.4.2)
	PR	Continue AZD4573 monotherapy (Period 1, Cycle 6) ^b	Period 1, after 8 cycles (Section 26.4.2)
	SD	Start combination therapy (Period 2, Cycle 1)	Period 2, after 2 cycles (Section 26.4.2)
	PD	Start combination therapy (Period 2, Cycle 1)	Period 2, after 2 cycles (Section 26.4.2)

^a Schedule the disease assessment to ensure availability of Lugano overall response ([Cheson et al 2014](#)) before Day 1 of the subsequent cycle.

^b AZD4573 + acalabrutinib combination treatment (Period 2, Cycle 1) can be started at the discretion of the investigator.

Note: AZD4573 + acalabrutinib combination treatment (Part A, Period 2) shall be started, if the participant develops PD at any time during the AZD4573 monotherapy (Part A, Period 1).

Abbreviations: CR = complete response; PD = progressive disease; PR = partial response; SD = stable disease.

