26.4.2 Disease Assessment Schedule

Baseline tumour assessments will be performed using radiologic imaging by CT with contrast and PET-CT during the screening period. CT scans with contrast will cover neck, chest, abdomen, pelvis and any other disease sites; PET scans will cover the whole body from base of skull to mid-thigh.

Radiologic scans (ie, contrast CT) and PET scans will be performed as specified in [Table 37](#) for Period 1, and [Table 38](#) for Period 2, to confirm PR/CR or as clinically indicated.

Unscheduled radiologic scans may be performed at Investigator discretion if deemed clinically indicated.

Table 37 Radiologic Scans and PET Scans for Tumour Assessments During AZD4573 Monotherapy (Period 1)

Timepoints		Required Radiologic Scans ^a	
Screening		Contrast CT	PET
During study ^b	After 8 weeks (~2 cycles) ^c	Contrast CT	
	After 17 weeks (~5 cycles) ^c	Contrast CT	PET
	After 26 weeks (~8 cycles)	Contrast CT	
	After 38 weeks (~12 cycles)	Contrast CT	PET
	After 50 weeks (~16 cycles)	Contrast CT	
	After 62 weeks (~20 cycles)	Contrast CT	PET
	After 74 weeks (~24 cycles)	Contrast CT	
	After 86 weeks (~28 cycles)	Contrast CT	PET
	Every 12 weeks (~4 cycles) thereafter until the end of the study	Contrast CT	
	Every 24 weeks (~8 cycles) thereafter until the end of the study	Contrast CT	PET
30-day Follow-up visit ^d		Contrast CT	PET

^a Following complete metabolic response, subsequent scheduled PET assessments are no longer mandatory.

^b Window of \pm 1 week for all timepoints.

^c Mandatory tumour assessments at 8 weeks and 17 weeks must be planned/scheduled to ensure availability of Lugano overall response ([Cheson et al 2014](#)) before starting Cycle 3 (Day 1) and Cycle 6 (Day 1), respectively.

^d Tumour assessments will be repeated at this visit for discontinued participants if not previously performed within the required timeframe ie 9 weeks for participants that discontinued before or during Week 26, and 12 weeks for those that discontinued after Week 26.

Note: At the time the participant moves from Period 1 AZD4573 monotherapy to Period 2 AZD4573 + acalabrutinib combination, contrast CT and PET should be performed.

Table 38 Radiologic Scans and PET Scans for Tumour Assessments During AZD4573 + Acalabrutinib Combination Therapy (Period 2)

Timepoints		Required Radiologic Scans ^a	
During study ^b	After 8 weeks (~2 cycles) ^c	Contrast CT	PET
	After 17 weeks (~5 cycles) ^c	Contrast CT	
	After 26 weeks (~8 cycles)	Contrast CT	PET

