27.2 Sample Size Determination

Approximately 12 participants will be treated with AZD4573 \pm acalabrutinib in this module.

The primary objective of Part A will be to assess safety and confirm the RP2D of AZD4573 monotherapy in MCL participants and assess the safety and tolerability of AZD4573 in combination with acalabrutinib in participants administered AZD4573 monotherapy. Anti-tumour activity will also be explored in Part A.

[figure not shown]
Even though the sample size is not based on the expected ORR, the following examples (Table 42) give an indication of the information obtained with response data from n=12 participants in Period 1 and n=11, 10, 9, 8, 7, and 6 participants in Period 2. For example, for CCI

Table 42

CCI

CCI

CCI

Note: Probabilities are calculated based on the CCI

Abbreviations: ORR = objective response rate; Pr = probability.

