27.4.5.4 Progression-Free Survival (PFS)

Disease progression will be determined by the investigators according to the revised response criteria for malignant lymphoma ([Cheson et al 2014](#)). PFS is defined as the time from first dose date to documented disease progression, or death (from any cause in the absence of progression), regardless of whether the participant withdraws from therapy or receives another anti-cancer therapy prior to progression. Participants who have not progressed or died at the time of analysis will be censored at the time of the latest date of assessment from their last evaluable disease assessment. However, if the participant progresses or dies immediately after 2 or more consecutive missed visits, the participant is censored at the time of the latest evaluable disease assessment prior to the 2 missed visits.

The PFS time will always be derived, based on scan/assessment dates, not visit dates.

Tumour assessments/scans contributing towards a particular visit may be performed on different dates. The following rules will be applied:

- Date of progression will be determined, based on the earliest of the dates of the component that triggered the progression.
- When censoring a participant for PFS, the participant will be censored at the latest of the dates contributing to a particular overall visit assessment.

Kaplan-Meier plots will be provided.

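### Module 2 ORR and PFS close at first progression, yet progression on monotherapy is one mandated route into the combination, so Period 2 activity is understated for those entrants

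*Protocol*

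**What the plan says.** Protocol Section 27.4.5.1 gives a single ORR definition for Module 2: "Data obtained from first dose of study treatment up until progression, or the last evaluable assessment in the absence of progression, will be included". Section 27.4.5.4 says: "PFS is defined as the time from first dose date to documented disease progression", or death. Section 27.4.5.2 times response (TTR) from first dose of study treatment, and Section 27.4.5.3 starts duration of response (DoR) at first objective response. None of these subsections separates Period 1 from Period 2.

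Section 24.4 governs the move to the combination. The note to Table 29 says that it "shall be started, if the participant develops PD at any time during the AZD4573 monotherapy". Table 29 also starts the combination for stable disease (SD) at the Cycle 5 assessment. Its footnote b allows the move, at the investigator's discretion, for SD at Cycle 2 or partial response (PR) at Cycle 5.

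The reporting intent is by period. Table 26 has an exploratory objective on the activity of AZD4573 alone and in combination. Section 27.4.5 says: "Tumour response data will be listed and summarised by treatment period". Section 27.2 illustrates "response data from n=12 participants in Period 1 and n=11, 10, 9, 8, 7, and 6 participants in Period 2". The note to Table 37 in Section 26.4.2 adds that "At the time the participant moves from Period 1 AZD4573 monotherapy to Period 2 AZD4573 + acalabrutinib combination, contrast CT and PET" should be done, but no text makes that scan a response baseline.

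**The concern.** For a participant who enters Period 2 because of PD, the event that opens the combination period also closes the ORR window and ends PFS. Every Period 2 scan comes afterwards. A complete or partial response on the combination in such a participant cannot be counted under Section 27.4.5.1, and Section 27.4.5.4 records only the PFS reached on monotherapy.

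The combination summary would then describe mainly the participants who crossed without PD, while those who had progressed on monotherapy stay in the denominator as non-responders whatever the combination did. Section 22.1 says that Part B will be designed from the data emerging from Part A, so a distorted Period 2 ORR would feed a later decision even though nothing is formally tested.

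**Working it through.** The protocol has no figure to reproduce: the Table 42 probabilities are redacted, and Section 27.2 says the sample size is not based on ORR. The consequence of the rule can be computed directly.

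**Routes into Period 2 (Table 29) against the literal window**

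| Status at the move | Move | Combination response inside the ORR window? |
|---|---|---|
| PD at any time in Period 1 | mandated | no |
| SD at Cycle 5 | mandated | yes |
| SD at Cycle 2 | investigator's discretion | yes |
| PR at Cycle 5 | investigator's discretion | already a responder, on monotherapy data |

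**Inputs**
- n = number starting Period 2. Section 27.2 considers 6 to 11.
- k = number of those entering on PD. Not given in the document, so a range is used.
- p = true combination ORR. Assumed, and taken to be the same for every entry route. Two values are used: 50%, and 81%, which is the ORR that Section 20.1 quotes for acalabrutinib alone in relapsed or refractory MCL. Neither is a prediction.

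**Formulas** for responses reached on the combination: highest countable ORR = (n − k)/n; expected countable ORR = p × (n − k)/n.

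**n = 10**

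| k | highest countable | expected, p = 50% | expected, p = 81% |
|---|---|---|---|
| 2 | 8/10 | 0.50 × 0.8 = 40% | 0.81 × 0.8 = 64.8% |
| 5 | 5/10 | 0.50 × 0.5 = 25% | 0.81 × 0.5 = 40.5% |
| 8 | 2/10 | 0.50 × 0.2 = 10% | 0.81 × 0.2 = 16.2% |
| 10 | 0/10 | 0% | 0% |

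A share of 25% would be 2.5 participants. It is taken as 2 here; 3 would give 0.50 × 0.7 = 35%.

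**Ends of the planned range, highest countable.** n = 11 with k = 3, 6, 8, 11: 8/11 (72.7%), 5/11 (45.5%), 3/11 (27.3%), 0/11. n = 6 with k = 2, 3, 4, 6: 4/6, 3/6, 2/6, 0/6.

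**Effect on the reported intervals** (exact Clopper–Pearson, at the two levels Section 27.4.5.1 asks for), n = 10 and p = 81%, about 8 true responders:
- Period-specific window: 8/10 = 80% (80% CI 55.0–94.5%; 95% CI 44.4–97.5%).
- Literal window with k = 5, about 4 counted: 4/10 = 40% (80% CI 18.8–64.6%; 95% CI 12.2–73.8%).
- Literal window with k = 10: 0/10 (95% CI 0–30.8%), whatever the combination does.

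**TTR and DoR.** TTR has no progression cut-off of its own, so a Period 2 response would have a value, but one timed from the first monotherapy dose and so including the whole of Period 1. At the first scheduled assessment that is already 35 + 21 = 56 days, or 8 weeks. DoR starts at the response itself and needs only that the response be assigned to a period.

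**The case against.** Four points can fairly be made against this.

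*The parent section already says by period.* Section 27.4.5 summarises response by treatment period, and reading the ORR window within each period is a natural way to give that effect. This shows the intent, and an analyst might well act on it. It does not reset the window, name a Period 2 baseline or state a denominator, and Section 27.4.5.1 as worded still stops at progression.

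*It belongs in the SAP.* Section 27.4.5 leaves the planned analysis of exploratory endpoints to the SAP, which is not at hand and may set period rules. But the protocol is not silent: it fixes a data window. A SAP that opened a second window after progression would depart from Section 27.4.5.1, not elaborate it.

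*The endpoints are exploratory.* This stands. The primary objectives are safety and dose confirmation, no hypothesis is tested, and the sample size does not rest on ORR. Section 18.5 in Module 1 also refers to a permanent halt of enrolment for the study, so it is unknown whether the Period 2 numbers in Section 27.2 will be reached.

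*The size is arithmetic on assumptions.* This stands too. The share entering on PD is unknown, response may differ by entry route, and the 81% comes from another treatment, whereas Section 23.1 also admits BTK-inhibitor-exposed participants. Someone who responded before progressing in Period 1 already counts under a study-long reading, though on monotherapy data.

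A reader might go further and infer that PD is the only way into Period 2, that the combination ORR is driven to 0 by definition, or that TTR and DoR become undefined. The documents support none of these. There are other mandated and discretionary routes; a value near 0 needs nearly all entrants to come through PD; and TTR has a poorly placed origin but still exists, while DoR is not timed from first dose at all.

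**Conclusion.** The point holds for participants who enter Period 2 on PD. For them Section 27.4.5.1 excludes any combination response and Section 27.4.5.4 has already ended PFS, against the stated aim of exploring the combination and reporting by period.

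The Period 2 ORR is reduced by the factor (n − k)/n. At n = 10 and a true ORR of 50%, that is an expected 40%, 25% or 0% for 2, 5 or 10 PD entrants. These figures assume the literal window, a denominator of all who start Period 2, and equal response across entry routes. The document gives no PD share, so they show direction and range and do not forecast a result.

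Severity is moderate: the stated rule gives a wrong summary if followed, but only for exploratory endpoints.

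**What to change.** Define the endpoints by period in Section 27.4.5 and carry the same wording into the SAP:

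- **Period 1:** screening baseline; data from first dose to the earlier of progression or first Period 2 dose.
- **Period 2:** transition CT/PET as baseline; data from first Period 2 dose to the first progression after it; TTR and PFS timed from first Period 2 dose.
- **Period 2 denominator:** all participants who start Period 2. A missing transition scan, or no response, counts as non-response. Limiting the denominator to those with a transition scan would drop treated participants, because Section 26.4.2 says only that the scan should be done.
- **Already in response at transition:** report these participants separately, so that a response reached on monotherapy is not read as a combination response.
- **Whole strategy:** PFS from first study dose may be kept as a separate, labelled summary.

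The cost is wording. The transition scans are already called for, no treatment rule changes, and no new data are needed.

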27.4.5.2 Time to Response (TTR)

Time to response is defined as the time from the first dose of study treatment to the first objective response observed for participants who achieved a CR or PR. The date of first documented response should coincide with that used for the DoR endpoint. TTR will not be defined for those participants who do not have a documented response. TTR data will be listed and summarised.

27.4.5.3 Duration of Response (DoR)

DoR is defined as the time from the first objective response to the time of documented disease progression or death due to any cause, whichever occurs first. KM curves and estimates may be presented, if appropriate.

27.4.5.4 Progression-Free Survival (PFS)

Disease progression will be determined by the investigators according to the revised response criteria for malignant lymphoma ([Cheson et al 2014](#)). PFS is defined as the time from first dose date to documented disease progression, or death (from any cause in the absence of progression), regardless of whether the participant withdraws from therapy or receives another anti-cancer therapy prior to progression. Participants who have not progressed or died at the time of analysis will be censored at the time of the latest date of assessment from their last evaluable disease assessment. However, if the participant progresses or dies immediately after 2 or more consecutive missed visits, the participant is censored at the time of the latest evaluable disease assessment prior to the 2 missed visits.

The PFS time will always be derived, based on scan/assessment dates, not visit dates.

Tumour assessments/scans contributing towards a particular visit may be performed on different dates. The following rules will be applied:

- Date of progression will be determined, based on the earliest of the dates of the component that triggered the progression.
- When censoring a participant for PFS, the participant will be censored at the latest of the dates contributing to a particular overall visit assessment.

Kaplan-Meier plots will be provided.

27.4.5.5 Overall Survival (OS)

Overall survival is defined as the time from first dose until date of death from any cause. Participants who have not died by the analysis data cut-off date will be censored at their last date known to be alive before the cut-off date. Participants known to be alive or dead after the data cut-off date will be censored at the data cut-off date. Participants who are

lost to follow-up will be censored at the date of the participant is last known to have been alive. KM curves and estimates may be presented, if appropriate.

27.4.6 Pharmacokinetics

Pharmacokinetic results are a secondary objective for Part A.

Plasma concentrations of AZD4573 plus acalabrutinib and its metabolite ACP-5862 will be summarised by nominal sample time. Plasma concentrations and derived PK parameters will be summarised by treatment period. Plasma concentrations and the derived PK parameters at each time point will be summarised according to treatment by the following summary statistics:

- The geometric mean (gmean)
- Coefficient of variation (CV)
- Gmean \pm standard deviation
- Arithmetic mean calculated using untransformed data
- Standard deviation calculated using untransformed data
- Minimum
- Median
- Maximum
- Number of observations

The PK data for AZD4573, acalabrutinib and its metabolite ACP-5862 will also be displayed graphically. Displays will include plasma concentration participant profiles (on the linear and log-scale) versus time and gmean concentration (\pm standard deviation) versus time, stratified by dose.

Scatter plots of PK parameters versus dose, or log-dose, will also be considered to assess dose proportionality.

Derived PK parameters to be determined include Cmax, AUC0-t, AUClast, AUC0-inf, tmax, and t1/2.

Additional PK parameters may be determined.

27.5 Safety Review Committee – Module 2

An SRC, which includes the principal investigators, is tasked with the review of the available safety data (AEs and available pharmacokinetics/pharmacodynamics [PKPD]

data) for AZD4573 alone or in combination with acalabrutinib. All decisions made by the SRC will be documented in writing in the form of meeting minutes.

The SRC will meet during Module 2, Part A after the first 6 participants have completed Period 1, Cycle 1, and again after the first 6 participants entering Period 2 have completed Cycle 1. The AZD4573 monotherapy RP2D established in DLBCL (12 mg once weekly; study D8230C00001) will be evaluated in MCL participants (Period 1), and safety and tolerability compared with the known safety profile in DLBCL participants to confirm the RP2D in the MCL population. The AZD4573 + acalabrutinib combination RP2D established in participants with DLBCL from Module 1 will be evaluated in MCL participants (Period 2) after receiving AZD4573 monotherapy RP2D in Period 1.

A proposed interpretation of the dose confirmation of the AZD4573 monotherapy RP2D and assessment of the AZD4573 + acalabrutinib RP2D safety data will be presented to the SRC, who will provide their recommendations on the continued development of AZD4573 monotherapy and/or in combination with acalabrutinib in MCL participants. This process will be further described in the SRC Charter.

The SRC will continue to monitor safety and tolerability data for all participants in Part A as described in the SRC Charter.

Please refer to Appendix [A 5](#) and the SRC Charter for further information on the SRC.

The decisions and decision-making of the SRC will be documented and provided to the investigators.

